Phase 1: Pre-Implementation (Months 0-8). The PHQ-9 and fidelity measures will be embedded in the EHR and the PHQ-9 linked to tablet computers for client completion to promote feasibility. Phase 2: Randomized Implementation Trial: Dynamic Waitlist Control (Months 8-38; Sites:  $N=12$ ; Clinicians:  $N=150$ ; Clients:  $N=500$ ; mixed within- & between-subjects design). MBC implementation will occur across 4 cohorts (2-4 sites) at early and later stages (each with 5-months active implementation, 10-months sustainment) to reduce confounds (timing) and increase feasibility (phased training). Both conditions will enact the 5 strategies within the active implementation period. We will use rapid ethnography (month 1) to synthesize the needs assessment data and develop the tailored content. Phase 3: Characterization of MBC Fidelity (Months 38-48). MBC fidelity will be coded, clinician and client fidelity reports will be triangulated, and sustainment will be evaluated.

**Specific Aims.** The hybrid design yields one co-primary aim (outcomes at the clinician- and client-levels) and two secondary exploratory aims in the context of a pragmatic trial (Thorpe et al., 2009).

**Aim 1:** To compare the effect of standardized versus tailored MBC implementation on clinician-level (**1a**) and client-level (**1b**) outcomes. We hypothesize that tailored implementation will outperform standardized in terms of (**H1a**) MBC fidelity, and (**H1b**) reducing client depression severity.

**Aim 2:** To identify contextual mediators of MBC fidelity. We hypothesize (**H2**) that contextual mediators (structure, norms, etc.) will be leveraged in the tailored condition, but serve as barriers in the standardized condition.

**Aim 3:** To explore the impact of MBC fidelity on client outcomes (Chambers et al. 2013). We hypothesize (**H3**) that adapted MBC protocols (tailored condition) will outperform weekly administration of PHQ-9s (standardized condition) with respect to clinically significant change in depression severity from intake to week 12.

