## **C. APPROACH**

**Overview.** Given the underwhelming use of MBC in community mental health settings coupled with the demand for performance outcome assessment (Affordable Care Act), this randomized implementation trial aims to compare the effectiveness of a standardized versus tailored approach to implementation of MBC with co-primary outcomes at the clinician (MBC fidelity) and client (depression severity) levels. We will randomize 12 sites of a large community mental health center (Centerstone) to early or later stage standardized or tailored implementation enrolling 150 clinicians and 500 depressed clients in a pragmatic trial (Thorpe et al., 2009). The main clinician level outcome is MBC fidelity, defined as (a) client completion of the PHQ-9, (b) clinician review of scores in the electronic health record, and (c) discussion of scores in session. Phase 1 (months 0-8) will interface the most widely used and validated depressive symptom severity measure (Patient Health Questionnaire-9 item; PHQ-9; [name], 2001) with the electronic health record; this measure is the main client level outcome. Phase 2 (months 8-38) constitutes the active implementation (5 months) and sustainment (10 months) phase. In both conditions, clients will have the option to complete the PHQ-9 on tablets in the waiting room prior to session, which will feed scores to clinicians via the electronic health record. Sites randomized to the standardized condition will begin with a baseline mixed methods needs assessment (for the purposes of putative mediator data collection) and receive the guideline that MBC is to be used in each session with a depressed client. The standardized condition will include manualized training and triweekly group consultation with experts to promote MBC fidelity and optimize its clinical utility. An implementation team (including a site administrator, opinion leader, MBC champion, and research personnel) will convene prior to each triweekly group consultation to review progress and troubleshoot problems. Sites randomized to the tailored condition will also begin with a needs assessment to identify contextual factors that may serve as barriers to the implementation (guided by the *Framework for Dissemination*; [name] et al., 2008; see C7). Training and triweekly group consultation will be tailored to address these barriers (e.g., clinician attitudes toward MBC). The implementation team (same composition as in standardized) will define a site-specific guideline for MBC use (e.g., monthly) and convene prior to each triweekly group consultation to troubleshoot MBC fidelity barriers. At the start of the active implementation across both conditions, depressed clients of participating clinicians will be enrolled to compare the effect of standardized versus tailored MBC implementation on client outcomes. Phase 3 (months 38-48) will characterize MBC fidelity using electronic health record data capture. The evaluation approach is guided by the *Framework for Dissemination* ([name] et al., 2008) and includes a baseline needs assessment, implementation/process evaluation (5 months into implementation), and outcome/impact evaluation (15 months into implementation). This design will allow for a direct test of the assumption that voltage drop in treatment outcomes occurs in the context of adapting the intervention to fit the context (Chambers et al., 2014), while simultaneously exploring the effect of standardized and tailored approaches to MBC implementation.

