**Aim 1: Hypotheses:** Tailored implementation will outperform standardized in terms of (H1a) fidelity. MBC clinician fidelity was evaluated with two variables: (1) whether the PHQ-9 was recorded in the EHR, and (2) among encounters for which the PHQ-9 was recorded, whether it was discussed. Both outcomes were modeled using generalized linear mixed models with a logit link function for a binary distribution using the lme4 package. All models included random intercepts for clinicians and patients. Models for both outcomes were constructed in an identical sequence. Models comparisons in the model-building sequence described below were evaluated using the Bayesian Information Criterion (BIC); the model with the better BIC was selected for presentation. Several unconditional growth models (i.e., models with only parameters for time) were fit (i.e., linear, quadratic, log-transformed number of months). After establishing the unconditional growth model, additional fixed effects were added in the following sequence: (1) group main effect and (2) group x time interaction. Finally, new versus existing patient status was investigated as a main effect using a dummy variable for new patient status and as a patient status x group interaction.

**Aim 2: Hypotheses:** Contextual mediators will be leveraged in the tailored condition, but serve as barriers in the standardized condition. Mediation models were fit to evaluate which contextual factors (based on clinician-completed surveys, Table 5; and, clinician selection of drop-down menu reasons for MBC deviations captured in the electronic health record) mediate the impact of the implementation condition on both clinician- and client-level outcomes. The two critical effects underlying mediation were evaluated in separate models: treatment condition predicts the mediator (path *a*) and the mediator predicts the outcome (path *b*). Specifically, mediators were assessed at the conclusion of the implementation window and the mediators were used to predict PHQ9 completion in the sustainment window. The *a* path was assessed using linear mixed models with Satterthwaite degrees of freedom

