implemented using the R lmerTest package with a random intercept for clinic. The b path was assessed using generalized linear mixed models with a logit link function for a binary distribution using the lme4 package. **Aim 3 Hypotheses:** Adapted MBC protocols (i.e., tailored condition) will outperform routine weekly administration of PHQ-9s (i.e., standardized condition) with respect to clinically significant change in depression severity from intake to week 12. Depression severity was analyzed using linear mixed models with Satterthwaite degrees of freedom implemented using the R lmerTest package. Multiple imputation was used to estimate missing values across 20 datasets in which 22.8% of patients did not complete the 12-week interview. We first assessed whether there was a change in PHQ-9 between intake and week 12 in a mixed model containing patient status as a covariate and random intercepts for patient and clinic. Next, implementation group was added to the model. In addition, number of sessions, number of sessions that the PHQ-9 was recorded, and number of sessions that the PHQ-9 was discussed were added to the model. We also examined the interactions between new patient status and the focal variables. **Power calculations.** A power analysis for the multilevel models for Aim 1 was assessed with Monte Carlo studies in which power is the proportion of significant effects (2-tailed  $\alpha$ ,  $p < .05$ ) for parameters of interest observed over repeated analyses of simulated data (Muthén & Muthén, 2002; Thoemmes, Reiser, & MacKinnon, 2010) using MPlus (version 7). For each model, 10,000 data sets were simulated and analyzed. Data in the Monte Carlo studies were simulated with the goal of identifying the smallest detectable effect size with power  $> 80$ . Dropout was simulated to reflect an increase of 5% missing data per wave. Repeated measurements were nested within participants (ICC = .50) and participants were nested in sites (ICC = .05). Average effect sizes for Aim 1 analyses were computed using an approximation of Cohen's  $d$  for growth models (Feingold, 2009). Using this metric, we are sufficiently powered to detect effect sizes as small as  $d = .46$  for the clinician models ( $N = 150$ ) and effect sizes as small as  $d = .30$  for the client models ( $N = 500$ ). For Aim 2, we conducted power analyses for the hypothesized mediation effects with the same assumptions described above but with the use of effective samples size estimates (an ICC corrected sample size) based on a design effect adjustment (Bickel, 2007) in order to use standard effect size metrics. The  $\kappa^2$  effect size for mediation (.01, .09, and .25 represent small, medium, and large  $\kappa^2$  respectively) was computed (Preacher & Kelly, 2011). We are sufficiently powered to detect effect sizes as small as  $\kappa^2 = .16$  for the clinician models and effect sizes as small as  $\kappa^2 = .10$  for the client models. For Aim 3 analyses, we are sufficiently powered to detect effect sizes as small as  $r = .27$  for clinicians and as small as  $r = .21$  for clients. The planned sample sizes are consistently sufficient for detecting medium effect sizes for clinician outcomes and small effect sizes for client outcomes, with the power to treat site as a random effect based 6 sites per condition (Atkins & Baldwin, 2013).

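### Aim 1 names no primary contrast and no multiplicity rule: five condition terms each read at two-sided .05 give about a 13–23% chance of some false difference, and about 6–12% of one favouring tailored

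*Combined protocol and SAP*

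**What the plan says.** Section A (Specific Aims) sets the structure: "The hybrid design yields one co-primary aim (outcomes at the clinician- and client-levels) and two secondary exploratory aims". The Overview in section C repeats it as "co-primary outcomes at the clinician (MBC fidelity) and client (depression severity) levels", and C15 says the same. The hypothesis is directional and joins H1a (fidelity) and H1b (depression) with 'and': "We hypothesize that tailored implementation will outperform standardized in terms of" those two outcomes.

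C13a, Aim 1, then gives the fidelity analysis: "MBC clinician fidelity was evaluated with two variables: (1) whether the PHQ-9 was recorded in the EHR", and, among recorded encounters, whether the score was discussed. In each model "additional fixed effects were added in the following sequence: (1) group main effect and (2) group x time interaction". A patient status by group interaction is examined afterwards. BIC chooses between models, and the one it prefers is presented. No p-value rule is given for the condition terms.

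No depression model appears under Aim 1. The only one is under Aim 3, where implementation group is added to a mixed model for the PHQ-9 at intake and week 12.

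The only error level is in C13a, Power calculations. There "power is the proportion of significant effects" at two-tailed .05, taken parameter by parameter. The simulations were run "with the goal of identifying the smallest detectable effect size with power" above 80%, and report d = .46 for the clinician models (N = 150) and d = .30 for the client models (N = 500).

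**The concern.** Aims 2 and 3 are labelled exploratory, so Aim 1 carries the trial's conclusion. As written, support for it could come from PHQ-9 recorded, PHQ-9 discussed, either condition-by-time term, or the depression contrast. Nothing says which of these counts, in what order, or at what level. A chance finding on any one could be reported as a condition difference at p < .05. A false difference in the other direction would matter too: C14 says that failure of the hypothesis would show that customization harms outcomes.

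If instead both levels must succeed, error is less of a problem but power is more of one, because the printed detectable effects are per model.

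**Working it through.** **Inputs.** From C13a: two-sided .05 per parameter; target power 80%; two fidelity outcomes with two condition terms each; one depression condition term; d = .46 and .30. Assumed, because the documents give neither: the correlation between test statistics (0 to .8, equal for all pairs) and the number of encounters (2,000 to 20,000).

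**1. The plan's own figures.** Without clustering, d = .46 with 75 clinicians per arm gives 80.4% power, and d = .30 with 250 clients per arm gives 91.8%. Now apply a site design effect of 1 + (m − 1) × .05. For clinicians m = 150/12 = 12.5, the design effect is 1.575 and power is 61.2%. For clients m = 500/12 = 41.7, the design effect is 3.03 and power is 48.6%. No single variant tried gives both printed figures. The simulated growth model is not fully specified, so they can be neither confirmed nor called wrong. They are used below only as a base for scaling.

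**2. Any false difference, every term read at .05.** For k independent tests the chance is 1 − .95^k. For correlated tests it is P(max |Z| > 1.96).

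| Tests | ρ = 0 | ρ = .5 | ρ = .8 |
|---|---|---|---|
| 3 (recorded, discussed, depression) | 14.3% | 12.5% | 9.8% |
| 5 (adding two condition-by-time terms) | 22.6% | 18.3% | 12.7% |

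**3. A false result favouring tailored.** Each two-sided test puts 2.5% in that direction, so the independent case is 1 − .975^k and the correlated case is P(max Z > 1.96).

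| Tests | ρ = 0 | ρ = .5 | ρ = .8 |
|---|---|---|---|
| 3 | 7.3% | 6.3% | 4.9% |
| 5 | 11.9% | 9.1% | 6.4% |

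Under any dependence, five tests cannot exceed 5 × 2.5% = 12.5%.

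**4. If BIC decides the fidelity terms.** One extra parameter improves BIC when its likelihood-ratio statistic exceeds ln n, so the implied threshold is P(χ²₁ > ln n).
- n = 2,000: ln n = 7.60, threshold .0058. Total with depression at .05: 1 − (1 − .0058)⁴ × .95 = 7.2%.
- n = 20,000: ln n = 9.90, threshold .0016. Total: 5.6%.

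In the tailored direction these become 3.6% and 2.8%. Independence is assumed. With only 500 rows the either-direction total would be 9.7%.

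**5. If both levels must succeed.** Suppose each level has one contrast at 80% power. Joint power is .80² = 64% at ρ = 0, 69% at ρ = .5 and 73% at ρ = .8.

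With no true difference at either level, and any of the four fidelity terms sufficing for H1a, the error is (1 − .95⁴) × .05 = .1855 × .05 = 0.9%. If depression truly differs and fidelity does not, the false fidelity finding that completes the pair has probability up to 18.5% in either direction, or 1 − .975⁴ = 9.6% favouring tailored.

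**6. After the fix.** Two contrasts at .025 each give 1 − .975² = 4.94% if independent, and at most 5%. Detectable effects grow by (2.241 + .842)/(1.960 + .842) = 1.10: .46 × 1.10 ≈ .51 and .30 × 1.10 ≈ .33.

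**The case against.** The strongest reply is that the plan never describes five tests at .05. C13a selects fidelity models by BIC, the .05 appears only as the definition of power in planning simulations, and condition and condition-by-time are nested steps towards one presented model per outcome. This stands in part, because under BIC gating the inflation is small. But choosing which model to present does not settle what counts as evidence for H1a, and the Aim 1 power is defined by p < .05. The plan does not say which criterion decides.

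Second, the count of five is not fixed. H1a and H1b are separately labelled, and whether to adjust across the two levels of a hybrid design is partly convention. Taking H1a alone, with one test per outcome, the error is at most about 10% in either direction and 5% favouring tailored. On the other side, counting the patient status by group terms gives seven tests, with 30.2% and 16.2% if independent.

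Third, the 'and' joining H1a and H1b may mean that both are required, which would hold error low when neither level differs. That is a fair reading, but the plan does not state it, and it leaves open which fidelity outcome and term would count.

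Two stronger inferences are tempting and should not be drawn. A reader might take 13–23% as the chance of a false claim that tailored outperforms. That range counts errors in both directions; the directional figure cannot pass 12.5%, and its single-test comparator is 2.5%, not 5%. A reader might also say that the plan contradicts its own figures whichever way co-primary is read. It does not: no familywise rate and no joint power is stated anywhere.

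**Conclusion.** The gap is real: the co-primary aim has several possible routes to support and no rule for combining them. Its size depends on a decision the plan leaves open.
- Every term read at two-sided .05: about 13–23% for any false condition difference, and about 6–12% for one favouring tailored.
- BIC gating the fidelity terms: about 6–7% in either direction.
- Both levels required: joint power of about 64–73%, with .46 and .30 remaining per-model figures.

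These results rest on the assumed correlations and encounter counts, and on each test holding its nominal level. This should be fixed. Confidence is medium, because the documents do not settle which reading applies.

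**What to change.** In C13a, Aim 1:
- Name one H1a contrast. Its scoring must be reconciled with C11 (Phase 3), which says fidelity at tailored sites has to reflect each site's own guideline. Raw recording per encounter would count a session as a miss even where a site's guideline did not call for a PHQ-9.
- Name one H1b contrast, the condition effect on PHQ-9 change from intake to week 12, and place it under Aim 1.
- State whether either or both must succeed.
- State that a p-value decides the two named contrasts, with BIC used only to choose the form of time.
- If either suffices, test the two with Holm at overall two-sided .05, or in a stated fixed sequence. If both are required, report joint power.
- Label discussion of scores, the other condition terms and the patient status interactions secondary or exploratory.

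In Power calculations, under Holm, restate the detectable effects at the first step (.025) as about d = .51 and .33. Under a fixed sequence the per-model figures stand.

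C13a is written in the past tense and already reports that 22.8% of patients missed the week-12 interview. New wording alone therefore cannot show that the rule preceded the data. State when it was set, mark it post hoc if that applies, and report all contrasts.

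The cost is text and, under Holm, a slightly stricter first threshold (detectable effects about 10% larger). No new data are needed.

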## C6. MBC Fidelity

In this proposal, fidelity to MBC is a three-level categorical variable defined by (a) client completion of the PHQ-9 (No=0, Yes=1), (b) clinician review of scores in the electronic health record (No=0, Yes=1), and (c) discussion of scores in session (No=0, Yes=1). The former two (PHQ-9 completion and clinician review of scores) will be automatically captured through the electronic health record. Clinicians will also check a box in the electronic health record progress note to indicate if they discussed scores in session, as this practice optimizes the effectiveness of MBC (Eisen, Dickey, & Sederer, 2000). Given the known limitations to clinician self-report, this latter fidelity criterion will also be assessed with client self-report via an automated telephone survey immediately after their session. In their first month of implementation, all clinicians (regardless of condition) will be asked to indicate factors they perceived to have limited MBC use. Through a drop-down menu embedded in the electronic health record progress note, clinicians will select contextual factors based on the literature (Dowrick et al., 2009; Garland, Kruse, & Aarons, 2003; Valenstein et al., 2009) and clinician-identified factors (from our pilot data); See Appendix for complete list of options (e.g. lack of time, client refused, clinician forgot).

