**Tailored Implementation Condition.** Tailored Implementation refers to the [responsive application of implementation strategies and content matched to determinants of practice \(i.e., barriers\) identified via a needs assessment](#). The same strategies outlined in the standardized condition will be employed in the tailored condition, but with content tailored to the site. The needs assessment will reveal contextual factors that may serve as barriers to the implementation process (focus groups will be analyzed using rapid ethnography methods; [C13b. Qualitative and Mixed Methods Data Analysis Plan](#)). An implementation team will convene to define the site-specific guidelines for PHQ-9 completion. For instance, it may be that Site X decides that monthly PHQ-9 administration is optimal with respect to feasibility and clinical utility. Conversely, Site Y may prefer to have clients complete the PHQ-9 every other session. Depressed clients of clinicians in the tailored condition will complete the PHQ-9 in the waiting room on a tablet computer prior to their appointment with the enrolled clinician based on the site-specific administration guideline. PHQ-9 data will then be fed to the electronic health record for clinician review. Training will be offered to all enrolled clinicians using tailored materials that will target the identified barriers from the needs assessment. For instance, if clinicians at a particular site perceive the PHQ-9 to be irrelevant to clients, training content will incorporate client perspectives on its utility. If clinicians indicate that lack of time is a barrier, then training will incorporate experimentation to streamline review and discussion of scores. The implementation team will focus on identifying remaining barriers for discussion in the triweekly group consultation session. Similar to the standardized condition, consultation will also focus on incorporating clinician review and discussion of PHQ-9 scores in session and providing tips on targeting lack of progress.

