
**Phase 3: Post Hoc Characterization of MBC Fidelity, Data Analysis, and Manuscript Preparation.** Consistent with the Dynamic Sustainability Framework (Chambers, Glasgow, & Stange, 2013), the approach to MBC implementation has the potential to be adapted by sites in the tailored condition. That is, early in the active implementation process (within the first month), the implementation team will generate a guideline for MBC implementation that is specific to their site. Characterizing fidelity for this condition will need to reflect the guideline established for

ACTIVITIES	Table 4. Study Activities			
	YEAR 1	YEAR 2	YEAR 3	YEAR 4
Study Phase	Phase 1	Phase 2		Phase 3
EHR Modifications				
Clinician Enrollment				
Randomization				
Clinician Assessment				
Active Implementation	Co1	Co2	Co3	Co4
Sustainment Monitoring		10-months for each cohort		
Client Enrollment & Assessment				
Rapid Ethnography				
Qualitative Coding				
Data Analyses				
Characterize MBC Fidelity				
Manuscript Preparation				

Note. Co = Cohort (2-4 sites with 1-2 randomized to each condition).

each site. For instance, if a site set a guideline to administer the PHQ-9 monthly for each client then actual administration will need to be confirmed monthly. Data capture from the electronic health record will also include whether or not the clinician reviewed the PHQ-9 scores prior to or in session. Finally, with respect to coding of MBC review in session the clinician self-report (via the electronic health record) and client report (via automated phone survey) will be triangulated. Concurrently, focus group data will be formally coded (see *C13b. Qualitative and Mixed Methods Data Analysis*) for manuscript preparation.

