**Data Collection.** The goal of client data collection is to determine if routine measurement (in the standardized condition) improves depressive symptom severity and whether adaptations to the MBC assessment schedule (tailored condition) have differential effects on depression outcomes. Clients will complete the PHQ-9 on a tablet kiosk in the waiting room according to site-generated guidelines; this information will be automatically fed into the electronic health record for clinicians to review in session. Given the potential for variable PHQ-9 completion in the tailored condition (based on the site-generated guideline), we will also have clients enrolled in both conditions complete the PHQ-9 at baseline (immediately post consent) and at week 12 of treatment (via automated phone survey). The 12-week window

reflects a commonly used time period in randomized clinical trials during which depressive symptoms are expected to remit. We will also supplement data collection with client 5-axis diagnoses and employment status captured in intake and progress review reports.

**Retention.** At recruitment, clients will complete a consent form and provide options for multiple contact methods (e.g. multiple phone numbers, address). Centerstone has consistently achieved greater than 75% client retention in federally-funded randomized trials (CATIE, Keefe et al., 2007; STAR\*D, Insel, 2006). We will replicate previous efforts to maximize retention in the proposed study. In order to have sufficient power to detect statistical significance and account for client attrition, we intend to recruit 1.25 more client participants ( $N=625$ ) to assure that we achieve our enrollment goal ( $N=500$ ).

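### H1a fidelity is defined in unreconciled ways: tailored fidelity is meant to follow each site's guideline, but the model scores a recorded PHQ-9 with no due rule and no stated denominator

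*Combined protocol and SAP*

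**What the plan says.** H1a is the clinician half of the co-primary aim. It predicts that tailored implementation will give better MBC fidelity than standardized. The combined protocol and SAP describes that fidelity in three ways.

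- **Plain completion.** A (Specific Aims), the Overview in C, C6, Table 5 (Section III) and Section VII all make completion of the PHQ-9 the first fidelity component. None of them says when completion was due.
- **Relative to the guideline.** C11, Phase 3, says of the tailored arm: "Characterizing fidelity for this condition will need to reflect the guideline established for" each site. Its example is that "if a site set a guideline to administer the PHQ-9 monthly for each client then actual administration will need to be confirmed monthly".
- **As modelled.** C13a, Aim 1, uses "1) whether the PHQ-9 was recorded in the EHR, and (2) among encounters for which the PHQ-9 was recorded, whether it was discussed". The fixed effects are time, group, group by time, and patient status. There is no guideline or due-session term, and no reference to the Phase 3 coding.

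The standardized guideline makes every session due (C8, Table 3). Tailored sites set their own. C10 gives monthly as one possibility and adds that "Site Y may prefer to have clients complete the PHQ-9 every other session". The documents do not report which guidelines the sites adopted.

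**The concern.** The Phase 3 rule exists because the arms may work to different schedules, yet no section carries that rule into the H1a model. On a per-encounter reading, a tailored site that follows a sparser guideline exactly would be scored as failing at every session where nothing was due. A difference in schedule could then be read as a difference in fidelity.

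The protocol saw this problem for the client outcome. C12b begins its reasoning with "Given the potential for variable PHQ-9 completion in the tailored condition (based on the site-generated guideline" and so adds PHQ-9 assessments at baseline and week 12 for all clients. H1a has no such safeguard. The risk of misreading is real, because C14 says that an unsupported hypothesis would be taken to show that customization harms outcomes. The Aim 2 mediation model also predicts PHQ-9 completion, with the same gap in definition.

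The second variable, discussion among encounters with a recorded PHQ-9, is restricted to a subset formed after randomisation. The site guideline can itself affect who is in that subset.

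**Working it through.** The plan states no figure that this point depends on. The detectable effect of d = 0.46 for the clinician models is for a growth metric, not for these binary variables.

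**Step 1: denominator.** C13a names encounters only in the second variable. Aim 3 then uses "number of sessions that the PHQ-9 was recorded, and number of sessions that the PHQ-9 was discussed were added to the model", which also counts by session. A per-encounter denominator for the first variable is the natural reading, but it is an inference.

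**Step 2: inputs.**
- f, the share of tailored encounters at which a PHQ-9 is due: 1/2 for every other session, 1/4 for every fourth session (monthly with weekly sessions). Session frequency is an assumption. With two-weekly sessions, monthly becomes roughly every other session.
- a, adherence at due encounters, taken as equal in both arms: 13.4% and 38.6%, the pilot's PHQ-9 use (C9), and 60%, an assumption. The pilot had no tablets and a minimal protocol, so its rates are only a guide.
- q, recording at tailored encounters where none is due: 0 unless stated. All tailored sites are on one schedule unless stated.

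**Step 3: formulas.** Tailored per-encounter rate t = f·a + (1 − f)·q. The standardized rate is a. Crude OR = [t/(1 − t)] / [a/(1 − a)]. Scored against the guideline, the OR is 1.00 throughout, because adherence is equal.

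**Step 4: ceiling.** With a = 100% and q = 0, t = f. The tailored arm scores 50% or 25% and the standardized arm 100%.

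**Step 5: equal adherence, q = 0.**

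| a | t, every other | OR | t, one in four | OR |
|---|---|---|---|---|
| 13.4% | 6.7% | 0.46 | 3.35% | 0.22 |
| 38.6% | 19.3% | 0.38 | 9.65% | 0.17 |
| 60% | 30% | 0.29 | 15% | 0.12 |

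For example, (0.30/0.70)/(0.60/0.40) = 0.286.

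**Step 6: what weakens the effect (a = 60%).**
- Off-schedule recording of q = 30%: t = 0.5 × 0.60 + 0.5 × 0.30 = 45%, OR 0.55. For one in four, t = 0.25 × 0.60 + 0.75 × 0.30 = 37.5%, OR 0.40.
- Only 2 of 6 equal-sized tailored sites go sparser, q = 0: (2 × 30 + 4 × 60)/6 = 50%, OR 0.67. For one in four, (2 × 15 + 4 × 60)/6 = 45%, OR 0.55.
- If q = a, or if all sites choose every session (f = 1), then t = a and the OR is 1.00.

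**Step 7: the opposite hazard.** Suppose per-session recording p is identical in both arms, but a tailored client-month counts as met if any of k sessions has a PHQ-9. The tailored rate is 1 − (1 − p)^k against p.
- k = 4: 43.8% v 13.4%, OR 5.0; 85.8% v 38.6%, OR 9.6; 97.4% v 60%, OR 25.
- k = 2: 25.0% v 13.4%, OR 2.2; 62.3% v 38.6%, OR 2.6; 84% v 60%, OR 3.5.

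An any-time-in-month window therefore favours the tailored arm even when behaviour is the same.

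**The case against.** The strongest reply is that C13a follows the definition the protocol uses most often. Five places define completion without a due rule, and the guideline rule appears only under the post hoc Phase 3 characterization. This stands. C13a does not break a single settled definition; the documents hold two, and nothing says which one H1a uses.

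A second reply is that a common per-encounter yardstick is a legitimate choice. It is a randomised comparison, whereas guideline scoring measures the arms against different standards, one of them chosen by the tailored sites after randomisation. This also stands, and it is why the per-encounter outcome should be kept. It does not justify calling that outcome fidelity while C11 says that tailored fidelity must reflect the guideline.

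Third, the Phase 3 coding may have been applied before modelling. That is possible, but C13a does not say so.

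A reader might go further and infer that the H1a result is distorted, or that a tailored arm with better fidelity was reported as worse. The documents do not support that. The denominator is inferred, the adopted guidelines are not reported, and no document gives adherence by arm.

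**Conclusion.** The point holds as a failure to reconcile definitions on a co-primary outcome, and it should be fixed. What is established is that the Phase 3 rule is not linked to the H1a model and that the first variable has no stated denominator. A shift in the estimate needs two further conditions: per-encounter scoring, and at least one tailored site on a sparser schedule. Monthly and every other session are the only tailored schedules the documents give as examples.

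With every tailored site sparser, equal adherence and no off-schedule recording, the crude OR is about 0.46 to 0.29 (every other session) or 0.22 to 0.12 (one in four) over adherence of 13.4% to 60%. It moves towards 1.00 with off-schedule recording or fewer sparse sites. These are crude illustrations. C13a fits mixed models with clinician and patient intercepts, so they do not predict its estimate.

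The direction is against H1a, so per-encounter scoring would not by this route create a false claim for tailoring. The harm is that a null or negative result could not be read as lower fidelity.

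**What to change.** 1. Reconcile C6, C11 (Phase 3) and C13a. State the denominator of the first variable and label the per-encounter result as PHQ-9 use.
2. Add one guideline-referenced outcome, in the same model: recorded yes or no on occasions due under each site's documented guideline, counted from the date the guideline was set. Take the due rules from implementation-team records, not from the recording data. C13a already reports that "22.8% of patients did not complete the 12-week interview", so if data have been analysed, label this a re-analysis.
3. State which of the two outcomes answers H1a and report the other as supporting. Do not read lower per-encounter use as lower fidelity. Do not claim superior tailored fidelity from the guideline-referenced outcome alone, because it rewards a lax guideline and a monthly window is lenient (Step 7).
4. Label discussion among recorded encounters as a comparison within a post-randomisation subset.

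The cost is revised wording, a written due rule for each tailored site, modest recoding of health-record data and one more reported outcome. Retrieving the rules may take some work: the documents describe barrier logs and recorded meetings, but no dated register of guidelines. Because guidelines are set during the first month, the earliest encounters may have no due rule.
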